10.2. Dose-Adjustment Criteria

No individualized dose adjustment is allowed during any part of the study except in the event of intolerability, for which a dose interruption or patient discontinuation may occur at the judgement of the Investigator in consultation with the Medical Monitor (see Section 10.2.1 below for details).

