10.2.1. Dose Interruption Safety Criteria and Management

Patients who experience hematologic adverse events as described in Table 3, significant clinical laboratory abnormality, or adverse events that may reflect an unfavorable risk-benefit profile may have their dose interrupted at the discretion of the Investigator. The Medical Monitor should be consulted whenever possible prior to decisions for dose interruption.

Patients who withdraw consent and therefore are discontinued from the study should undergo an Early Termination Visit and subsequent Safety Follow-up Visit as appropriate per Section 9.3.1 Patient Withdrawal Procedures, and associated adverse events followed as described in Section 12 Adverse Events.

Hematology parameters will be assessed bi-weekly for the first 4 weeks of the Treatment Period, and every 4 weeks thereafter for the remainder of the study. Prior to dose interruption, hematology parameters should be confirmed with repeat testing at an Unscheduled Visit within 72 hours, except in severe cases (i.e.: neutrophil counts below 0.5 x 10⁹/L) where immediate interruption of dosing is necessary for the safety of the patient. Blood draws confirming dose interruption criteria should occur prior to the first daily dose on the day of draw.

Dose interruption requirements for hematologic abnormalities are provided below. However, less significant changes may warrant clinical intervention and the Investigator should use his/her best clinical judgment when considering a dose interruption whether for singular or aggregate

hematology results above the limits provided in Table 3, or for other clinical signs, symptoms, or considerations that suggest dose interruption is in the best interest of the patient.

Table 3: Selected Hematologic Thresholds for Dose Interruption

Neutrophil Count	Dose Adjustment
Between 0.5 to 1 x 10 ⁹ /L	Interrupt dose until recovered to greater than 1.5 x 10 ⁹ /L and
(Grade 3)	resume dosing at previous dose
Less than 0.5 x 10 ⁹ /L (Grade 4)	Severe case: Interrupt dose immediately and repeat CBC with differential within 72 hours. Recommend hematology consult and contact medical monitor. Permanent discontinuation of treatment should occur upon repeat confirmation of value
Female Hemoglobin Level	Dose Adjustment
Less than 10 g/dL	Interrupt dose until recovered to greater than 10.5 g/dL and resume dosing at previous dose
Male Hemoglobin Level	Dose Adjustment

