Less than 11.5 g/dL	Interrupt dose until recovered to greater than 12 g/dL and resume dosing at previous dose
Platelet Count	Dose Adjustment
Less than 75 x 10 ⁹ /L	Interrupt dose until recovered to greater than 100 x 10 ⁹ /L and resume dosing at previous dose
Greater than 750 x 10 ⁹ /L	Interrupt dose until recovered to less than 600 x 10 ⁹ /L and resume dosing as prescribed by the Investigator

Upon dose interruption, the parameters that triggered the interruption should be monitored at least weekly until either: 1) recovery above the threshold for dosing resumption is achieved, or 2) a 21-day dose interruption period has elapsed, at which time a discussion between the PI and the Medical Monitor should occur to evaluate whether or not the subject should discontinue treatment permanently. In the case of severe neutropenia (neutrophil counts less than 0.5 x $10^9/L$) patient should interrupt dose **immediately** and repeat CBC with differential within 72 hours. The Medical Monitor should be contacted and a hematology consult should be made if appropriate. Permanent discontinuation of treatment should occur upon repeat confirmation of value. Patients who discontinue treatment due to lack of acceptable recovery of parameters should continue to be followed for all safety and efficacy assessments through the completion of the 24-week treatment period, and will have all endpoints (including efficacy) collected accordingly.

Subjects with both a positive SARS-CoV-2 test (antigen or antibody) AND signs or symptoms consistent with SARS-CoV-2 infection should immediately interrupt dosing with study drug. Dose interruption should continue until symptoms subside (it is not necessary to have a negative SARS-CoV-2 test result). If symptoms do not subside within a 21-day dose interruption period, a discussion between the PI and the Medical Monitor should occur to evaluate whether or not the subject should discontinue treatment permanently. Signs and symptoms include, but are not limited to: fever or chills, cough, shortness of breath or difficulty breathing, fatigue, muscle or body aches, headache, new loss of taste or smell, sore throat, congestion or runny nose, nausea or

vomiting, diarrhea, trouble breathing, persistent pain or pressure in the chest, new confusion, inability to wake or stay awake, bluish lips or face.

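### The hematologic dose-interruption rules in Protocol Sections 10.2 and 10.2.1 disagree in three places: the direction of the monitoring stop rule, the restart wording for high platelets, and whether Table 3 is discretionary or required

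*Protocol*

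**What the plan says.** Section 10.2 of the protocol sets the general rule: "No individualized dose adjustment is allowed during any part of the study except in the event of intolerability", and the exception is one "for which a dose interruption or patient discontinuation may occur at the judgement of the Investigator in consultation with the Medical Monitor". It refers to Section 10.2.1 for details.

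Section 10.2.1 opens by saying that patients with the hematologic events in Table 3, with other significant laboratory abnormalities, or with certain adverse events "may have their dose interrupted at the discretion of the Investigator". Two paragraphs later it says: "Dose interruption requirements for hematologic abnormalities are provided below".

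Table 3 has six threshold rows. Four of them (neutrophils 0.5 to 1, low hemoglobin in women, low hemoglobin in men, low platelets) give a level that the value must rise above and then restart at the previous dose. The row for neutrophils below 0.5 leads to permanent discontinuation once a repeat test confirms the value. The sixth row is triggered by a platelet count "Greater than 750" x 10^9/L. Its instruction is "Interrupt dose until recovered to less than 600" x 10^9/L and then "resume dosing as prescribed by the Investigator".

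The text after the table applies to every triggering parameter. Monitoring is at least weekly until either "recovery above the threshold for dosing resumption is achieved" or 21 days have passed, when the site and the Medical Monitor discuss permanent discontinuation.

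**The concern.** Site staff apply this text directly when a safety laboratory result comes back, so they should not have to work out which of two statements governs.

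- **Stop rule.** One sentence covers both directions of recovery but names only one. In the row where recovery means a fall, it points the opposite way from the row.
- **Restart wording.** One row departs, without explanation, from the other four restart rows and is open-ended where Section 10.2 is restrictive. The Period 2 arms are defined by dose and are expected to hold about 25 patients each (Section 13.1), so a restart off the assigned dose would matter there if it happened.
- **Discretion or requirement.** Two sites could act differently on the same count and each cite the protocol.

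**Working it through.** The plan gives no figure to reproduce here. The check is one of logic, with inputs from Table 3 and the stop rule in Section 10.2.1.

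**Stop rule.** For each row with a restart level T, take values x that trigger interruption. Ask whether x > T (the literal stop rule) and whether x meets the row's own restart criterion. Platelets and neutrophils are in 10^9/L, hemoglobin in g/dL.

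| Row | Trigger | Restart criterion | Values tried | x > T? | Row's criterion met? |
|---|---|---|---|---|---|
| Neutrophils | 0.5 to 1 | > 1.5 | 0.5, 0.75, 1.0 | No | No |
| Hemoglobin, women | < 10 | > 10.5 | 8, 9.9 | No | No |
| Hemoglobin, men | < 11.5 | > 12 | 9, 11.4 | No | No |
| Platelets, low | < 75 | > 100 | 30, 74 | No | No |
| Platelets, high | > 750 | < 600 | 751, 800, 1000 | Yes | No |

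In the four low-value rows the trigger lies below T (1 < 1.5, 10 < 10.5, 11.5 < 12, 75 < 100), so the stop rule and the restart criterion agree. In the high-platelet row 750 > 600, so every triggering count exceeds T while failing the row's criterion. Follow-up counts show the same reversal: 601 and 700 are above 600 but do not permit restart, while 599 permits restart but is not above 600.

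Section 10.2.1 has a second sign of one-directional drafting. It describes less serious changes as results above the Table 3 limits. That fits low counts, but a less serious high platelet count lies below 750.

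**What the literal reading could cost.** Hematology otherwise runs every 4 weeks after the first month of treatment. In a 28-day interval starting at a scheduled visit, the weekly checks that could be lost fall on days 7, 14 and 21: 28/7 − 1 = 3 checks, all while drug is held.

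**Restart wording, side by side.** Section 10.2 allows interruption or discontinuation and lists no change of dose on restart. Four Table 3 rows agree with it by naming the previous dose. The high-platelet row names no dose and refers to the Investigator's prescription. The reference in Section 10.2 to Section 10.2.1 for details does not widen its exception.

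**Discretion or requirement, side by side.** The opening sentence of Section 10.2.1 is permissive and expressly includes Table 3 events, and Section 10.2 is permissive too. The later sentence calls the table's contents requirements, and its rows are written as instructions. The text then reserves the Investigator's judgment for less significant changes, which implies that the table itself is not a matter of judgment.

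**The case against.** A reader might infer that a patient with a count over 750 satisfies the stop rule on the day of interruption and so leaves monitoring, or resumes drug, while still high. The documents do not support that. The sentence requires recovery, and the row just above it defines recovery for this parameter as a fall below 600, so the intent is recoverable. Drug stays held until the row's criterion is met, which needs a further count. Scheduled hematology continues, Section 11.11 provides Unscheduled Visits to confirm results before dosing resumes, and Section 9.3 separately sends interruptions longer than 21 days to the Medical Monitor. What stands is that the stated direction contradicts the row and a reader has to repair it.

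A reader might also infer that patients can restart on a dose outside their randomized arm. That too goes beyond the text. The row mentions no different dose, and it can be read together with Section 10.2 as the Investigator directing when dosing resumes. Sites are blinded throughout (SAP Section 7.2), tablets are identical in appearance (Section 8.3), and the instruction is one tablet morning and evening (Section 10.4.3). No passage gives a blinded site a way to choose another strength. What stands is that the wording, unlike that of the other four rows, leaves the possibility open.

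On discretion, the permissive sentence also covers events outside Table 3, and reading the specific table over the general opening removes much of the tension. It does not remove all of it, because the permissive sentence names Table 3.

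**Conclusion.** The three inconsistencies are present in the current text, and all three are faults of wording in safety instructions. The stop-rule and restart limbs affect one of the six Table 3 rows; the discretion limb affects the table as a whole. The worst consequence the text allows on the first limb is a lapse of about three weekly checks while the patient is off drug. That figure assumes a literal reading and an interruption starting at a scheduled visit on the 4-weekly schedule. On the second limb, a different restart dose is only not excluded. On the third, handling may vary between sites.

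The documents give no frequency of platelet counts above 750. Screening excludes counts above 600 (Exclusion Criterion 13), so a patient must rise past 750 on study to reach the row, and few are likely to. Nothing here touches sample size, error rates or the planned analyses. The point is worth correcting because it sits in operative safety text and costs little to put right.

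**What to change.** Reconcile Section 10.2, Table 3 and the surrounding text of Section 10.2.1 so that:

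1. the direction in the monitoring stop rule matches the restart criterion of each row;
2. the high-platelet restart wording and Section 10.2 agree with each other;
3. interruption for Table 3 events is described consistently, either as discretionary or as required.

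Which version stands in each case is for the sponsor's medical team to decide; this review proposes no clinical rule. The cost is a few words in a protocol amendment or a clarification letter to sites, with no change to the SAP.

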10.3. Treatment Compliance

At each scheduled study visit after randomization, the Investigator or designee will interview the patient regarding treatment compliance and compare the number of dispensed versus returned study drug tablets. Patients should strive for 100% compliance with the daily dosing schedule. Retraining on treatment compliance should occur for patients with less than 80% compliance at any visit and the Sponsor should be notified.

10.4. Study Drug Materials and Management

Please consult the Pharmacy Manual for a complete description of the study drug and requirements for storage, handling, dispensing, accountability, returns and destruction.

10.4.1. Physical Description of Study Drug

Study drug will include CTP-543 and matching placebo. Details regarding formulation and dosage are presented in Table 5.

Table 5: Investigational Product

	Investigational Product (CTP-543 or Placebo)
Product Name:	CTP-543 or Matching placebo
Dosage Form:	Tablet
Dosage Strength of CTP-543	4 mg, 8 mg, 12 mg
Route of Administration	Oral
Physical Description	White, capsule-shaped tablets

10.4.2. Study Drug Packaging, Labeling, and Storage

Study drug will be packaged and labeled by an appropriately qualified vendor. Each patient will receive one 60 count bottle of study medication at each 4-week study visit. Details of the packaging, labeling and dispensing instructions can be found in the Pharmacy Manual.

The label(s) for the investigational product and placebo will include the required caution statements and/or regulatory statements, as applicable per local regulations.

Adequate supplies of study drug will be provided to each site by the sponsor or designee. Study drug should be stored in the original container between 15°C to 25°C (59°F to 77°F), as stated on the product label, in a secure, temperature-monitored, locked area, under the responsibility of the Investigator or other authorized individual until dispensed to the patients.

Study drug dispensed to patients should be stored in the original bottle at room temperature as stated on the package label. No special handling procedures are required. Due to the COVID-19 pandemic, Direct to Patient (DTP) shipping services may be warranted in cases where a patient is not able to attend in clinic visits or a site is closed. Additional information can be found in the Pharmacy Manual.

10.4.3. Study Drug Preparation and Administration

No study drug preparation is required. Patients will take the first dose of study drug in the clinic on Day 1 and will be instructed to take study drug approximately every 12 hours for the duration of the Treatment Period. If patients should dose study drug in the clinic on Study Visit Days dosing should be after clinical laboratory blood draws are completed.

Study drug should be taken at approximately the same times each day, with water, and without regard to food. Patients should be instructed to take one tablet in the morning and one tablet in the evening, approximately 12 hours apart. If a dose is missed, the patient should skip the missed dose and resume dosing at the next scheduled dose. The patient should not take two doses at the same time. Deviations from prescribed dosing should be discussed at each visit for assessment of compliance and retraining when necessary.

10.4.4. Study Drug Return and Disposal

The Sponsor (or designee) will review with the Investigator and relevant site personnel the process for study treatment return, disposal, and/or destruction, including responsibilities for the site versus the Sponsor (or designee). Specific requirements for destruction or return are defined in the Pharmacy Manual.

10.4.5. Study Drug Accountability

To satisfy regulatory requirements regarding drug accountability, all study drug will be reconciled in full. The Investigator or designee must maintain accurate records of the receipt of study drug, including date received, lot number, amount received, condition of the package, and the disposition of study drug.

Current dispensing records will also be maintained, including the date and amount of medication dispensed to each individual patient. Returned study drug records will be maintained and final study drug reconciliation will also be recorded for each patient.

10.5. Concomitant Medications and Procedures

All medications, including over-the-counter therapies (e.g., vitamins, herbal, and nutritional supplements) and vaccinations (including the SARS-CoV-2 vaccination), taken at the time of the Screening Visit through the patient's last visit will be recorded in the patient's source documentation and documented in the eCRF. Additionally, any prior janus kinase (JAK) inhibitor use or live virus vaccinations (including Herpes Zoster) will be recorded.

To date, there is no clear evidence of any safety concern for receipt of a SARS-CoV-2 vaccine during the treatment period. Existing data on JAK inhibitors and vaccines, including the SARS-CoV-2 vaccine, are insufficient to conclude whether JAK inhibitors, including CTP-543, have an effect on vaccine effectiveness, though data to date do not suggest that a major effect is likely. Subjects considering enrollment in this CP543.2004 trial may wish to receive their vaccine(s) before entering the trial. As subject and public health are paramount, SARS-CoV-2 vaccination should not be delayed or withheld for subjects already enrolled in the CTP-543 trial.

Knowledge about the vaccines and virus is continually growing. The Sponsor or will notify sites as new information is obtained that might further inform vaccine-related questions during the study. Please also carefully read the product information (package insert) for the vaccine being used, noting any specific precautions or warnings for concomitant administration with JAK inhibitors or immunosuppressants.

Any concomitant medication deemed necessary for the wellbeing of the patient may be given at the discretion of the Investigator. Use of medications that are prohibited per protocol will require patient withdrawal from the study. However, under certain circumstances, and in consultation with the Medical Monitor, short-term use of a prohibited medication may not necessitate withdrawal when its use is unlikely to unfavorably alter the risk-benefit of subject participation or confound the study endpoints.

The following treatments are not permitted during the study:

- Medications that may affect hair regrowth or immune response (such as: corticosteroids administered orally, by injection, or applied to areas of skin affected by alopecia; platelet-rich injections; topical application to affected areas of anthralin, squaric acid, diphenylcyclopropenone, or minoxidil;
- Chronic or long-term treatment with systemic immunosuppressive medications
 including but not limited to methotrexate, cyclosporine, and azathioprine; chloroquine
 derivatives; Janus kinase inhibitors (ruxolitinib, tofacitinib, etc), etanercept; or
 biologics (adalimumab, atlizumab, canakinumab, certolizumab, fontolizumab,
 golimumab, infliximab, mepolizumab, rituximab, secukinumab, tocilizumab,
 ustekinumab);
 - NOTE: a short course of steroid treatment for acute treatment of a condition during the trial may be allowed following discussion with the Medical Monitor
- Use of strong CYP3A4 inhibitors (such as, but not limited to clarithromycin, conivaptan, grapefruit juice, indinavir, itraconazole, ketoconazole, lopinavir/ritonavir, mibefradil, nefazodone, nelfinavir, posaconazole, saquinavir, telaprevir, telithromycin, voriconazole, or fluconazole) dosed for systemic exposure;

- Use of strong CYP3A4 inducers (such as, but not limited to barbiturates, carbamazepine, efavirenz, glucocorticoids, modafinil, nevirapine, oxcarbazepine, phenobarbital, phenytoin, pioglitazone, rifabutin, rifampin, St. John's Wort, or troglitazone) dosed for systemic exposure.
- Live vaccines including, but are not limited to) the measles, mumps, and rubella (MMR) vaccine; intranasal flu vaccine; and Zostavax (but not Shingrix) for herpes zoster.

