9.3. Patient Withdrawal Criteria

For all patients, it is the intent that patients who discontinue study medication (at any time) for any reason but do not withdraw consent will continue to be followed for all protocol-planned study visits through the completion of the 24-week treatment period, and will have all endpoints (including efficacy) collected accordingly.

The Investigator, Sponsor, or its designee may decide a patient should discontinue treatment at any time and for any reason. In addition, patients will discontinue randomized treatment if they:

- Experience an intolerable adverse event: such events include, but are not limited to, adverse event ≥ Grade 4*, bone marrow-related events, a ≥ Grade 3* cardiac event (*CTCAE v5.0 criteria);
- Require a medication that is prohibited by the protocol. However, under certain circumstances, and in consultation with the Medical Monitor, short-term use of a prohibited medication may not necessitate withdrawal of treatment when its use is unlikely to unfavorably alter the risk-benefit of subject participation;
- In the opinion of the Investigator, have any medically appropriate reason;
- Become pregnant;
- Have a serious adverse event associated with a SARS-CoV-2 infection;
- The Investigator believes that further treatment is undesirable or the risk-benefit profile has become unfavorable.

Furthermore, dose interruptions lasting more than 21 days may require treatment discontinuation on a case by case basis following consultation with the Medical Monitor.

In addition, patients are free to withdraw from participation in the study at any time, for any reason, and without prejudice. The Investigator must withdraw any patient from the study if the patient withdraws consent and requests to stop participating in the study.

Patients who withdraw or are withdrawn from the study will not be replaced.

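### Protocol 10.5 takes prohibited-medication users out of the study, while 9.3 only stops study drug and keeps following them; 10.5 should be aligned with 9.3.

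*Protocol*

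**What the plan says.** Protocol 10.5 (Concomitant Medications and Procedures): "Use of medications that are prohibited per protocol will require patient withdrawal from the study". The exception is short-term use, in consultation with the Medical Monitor, when it is "unlikely to unfavorably alter the risk-benefit of subject participation or confound the study endpoints". The list of barred treatments opens with "Medications that may affect hair regrowth or immune response", and a note adds that "a short course of steroid treatment for acute treatment of a condition during the trial may be allowed following discussion with the Medical Monitor".

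Protocol 9.3 (Patient Withdrawal Criteria) says that "patients will discontinue randomized treatment if they" meet any of several conditions, one of which is "Require a medication that is prohibited by the protocol". Its exception is that "short-term use of a prohibited medication may not necessitate withdrawal of treatment". The same section opens with a rule for all patients: those who stop study medication "for any reason but do not withdraw consent will continue to be followed for all protocol-planned study visits", through the end of the 24-week treatment period, with efficacy endpoints collected.

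On analysis, SAP 8.2.1 classifies each Period 2 patient by the last observed non-missing SALT and otherwise imputes nothing. SAP 8.5.1 censors a patient who leaves Period 2 early without LOM at the last visit with a SALT measurement. Neither has a rule for prohibited medication, and SAP 8.2.3 specifies no sensitivity analysis.

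**The concern.** One event has two prescribed actions. A site reading 10.5 ends the patient's participation; a site reading 9.3 stops the tablets and keeps the visits. The exceptions do not reconcile them, because both cover only short-term use and they excuse different things: withdrawal in 10.5, withdrawal of treatment in 9.3. The SAP's primacy clause (SAP Section 2) concerns analyses, so it does not tell a site what to do.

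What is at stake is follow-up for the Period 2 co-primary percentages. Under 10.5, SALT values that 9.3 intends to collect are never taken. A patient who leaves with SALT ≤20 is then reported as having maintained regrowth without being observed to Week 24.

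**Working it through.** **The two rules side by side, for use outside the short-term exception in Period 2**

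| | Following 10.5 | Following 9.3 |
|---|---|---|
| Study drug | stopped | stopped |
| Participation | ends | continues unless consent is withdrawn |
| SALT | at most an exit value (Table 1, footnote 4: the Week 48 visit, which includes SALT, doubles as the Early Termination Visit) | scheduled visits to the end of the 24 weeks |
| Exit SALT >20 | LOM | LOM |
| Last SALT ≤20 at exit | maintained (SAP 8.2.1); censored (SAP 8.5.1) | classified by later SALT |

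What 10.5 loses is therefore SALT after exit. The SALT at exit is still planned.

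**Arm size.** Protocol 13.1 plans 170 + 130 = 300 patients and about 50 Responders per dose group. Split 1:1 (Protocol 8.3), that is 50/2 = 25 per Period 2 arm, which reproduces the plan's figure.

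**Weight of one patient.** 1/25 = 4.0 points; 1/20 = 5.0 and 1/30 = 3.3 if arms come out smaller or larger.

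**Illustration.** Neither the LOM rate nor the number of users is in the documents. Assume 10 LOM in 25, plus k users who leave under 10.5 with SALT ≤20.

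- As planned: 10/25 = 40.0% for any k.
- If all k would have reached LOM under continued follow-up: 11/25 = 44.0% (k = 1), 12/25 = 48.0% (k = 2), 13/25 = 52.0% (k = 3).
- If none would have: still 40.0%.

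The gap per arm therefore runs from 0 to 4.0 points for one user and from 0 to 12.0 for three.

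**Kaplan-Meier LOM at Week 24.** Assume 2 LOM at each of Weeks 8, 12, 16, 20 and 24, and one user censored at exit.

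- Exit at Week 4: 1 − 14/24 = 41.7%.
- Exit at Week 8: 1 − (23/25)(14/22) = 41.5%.
- Exit at Week 20: 1 − (17/25)(14/16) = 40.5%.
- Followed and reaching LOM: 11/25 = 44.0%.
- Followed and maintained: 10/25 = 40.0%.

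**Scale.** The planned interval (SAP 8.2.2, Wald with continuity correction) at 10/25 has half-width 1.96 × √(0.4 × 0.6/25) + 1/50 = 19.2 + 2.0 = 21.2 points, so it runs from 18.8% to 61.2%. One patient's 4.0 points is under a fifth of the half-width.

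**The case against.** The best defence is that 9.3 is the governing section on withdrawal. It opens with a rule for all patients, and the same follow-up principle appears for other triggers in the Synopsis, 8.1 and 10.2.1. On that view 10.5 is one stray sentence, and it is not shown that sites would follow it. This makes clear which sentence to change. It does not remove the conflict, because 10.5 is current text in the section a site consults when a patient starts a medicine.

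Three stronger readings are tempting, and the documents do not support them.

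- *The co-primary LOM percentages are biased downward.* The direction is not fixed. A patient followed under 9.3 may hold SALT ≤20 because of the prohibited medicine, or lose it because study drug was stopped.
- *The SAP must recode these patients as LOM.* Such an analysis can only raise LOM. It would also single out one kind of early leaver, although the last-value rule in SAP 8.2.1 applies equally to those who leave for adverse events or withdrawn consent. Applied to everyone who leaves over a prohibited drug, it would count a patient on a strong CYP3A4 inhibitor or given a live vaccine as having lost hair. Planning no sensitivity analysis is an explicit choice in a descriptive study.
- *The reader cannot see these patients.* The abbreviated report includes Period 2 disposition with reasons for stopping treatment and study (Table 14.1.1.2), protocol deviations, medication listings and SALT over time (Listing 16.2.6.1.3). At about 25 per arm, a reader with these outputs can trace cases by hand. They do not recover SALT that was never taken.

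**Conclusion.** The conflict between 10.5 and 9.3 is real and unresolved for prohibited use outside the agreed short-term exception. Its consequence is narrow: loss of SALT after exit, with a last value ≤20 standing as maintained in the co-primary table and censored in the time-to-LOM analysis. Each such patient carries 4.0 points in an arm of 25. The illustrations above rest on assumed counts.

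The number of patients is unknown and probably small, because short-term use, including short steroid courses, is excepted, and because SALT >20 at any Period 2 assessment already returns the patient to the Period 1 dose. No hypothesis test is affected. Severity is minor: a wording correction that protects data the protocol already intends to collect. Confidence is high on the conflict; the size in practice cannot be known from the documents.

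**What to change.** In Protocol 10.5, replace the requirement to withdraw the patient from the study with: *discontinuation of study drug, with continued follow-up per Section 9.3*. Keep the short-term exception, including its condition about not confounding the endpoints. No new visits are needed.

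**Cost.** A small amendment, which must have IRB approval before sites apply it (Protocol 14.4). Some added SALT values will come after study drug was stopped, which can raise LOM in a dose-reduction arm. Others will come after a hair-affecting medicine was started, which can lower it.

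**Optional, not part of the required change.** A sensitivity analysis under SAP 8.2.3 could count as LOM those Period 2 patients who start a hair-affecting prohibited medicine before LOM, with matching event coding in a supporting Kaplan-Meier analysis. If added, the definition should include the medicines named in exclusion criterion 2, such as oral retinoids and oral cyclines, which the 10.5 list does not name. It should not recode patients who leave over other prohibited drugs. Patients should be flagged without treatment codes before the Part A freeze, and the number recoded shown per arm. It would still be one-directional and may count as LOM a patient who would have maintained.
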